## Background and Rationale

Neurofibromatosis 1 (NF1) is the most common type of neurofibromatosis with a broad spectrum of clinical manifestations in multiple organs of the body, including benign and malignant tumors (1–3). This autosomal dominant disease arises from several thousand genetic variants in the chromosome 17, but about 50% of the mutations are de novo (25). Moreover, mitochondrial DNA mutations in the loop region of the genome were seen in 37% of cutaneous neurofibromas and in 50% of plexiform neurofibromas, as also in non-tumor cells like non-affected skin cells (28). Although it is unclear if those mitochondrial mutations have functional effects, other evidence implicates that the impairment of neurofibromin causes mitochondrial dysfunction (MD).

The relation between neurofibromin and mitochondria is structural and functional. Neurofibromin can be co-localized within and extracted from mitochondria (26). Losing neurofibromin, guanosine-5'-triphosphate (GTP) hydrolysis decreases, activating RAS, a protein complex that stimulates mitochondrial degradation (27). Neurofibromin might also modulate mitochondrial respiration. Animal models showed mitochondrial respiration inhibition characterized by increased superoxide anion production and decreased adenosine triphosphate (ATP) generation that was reverted with transgene expression of neurofibromin (9). Loss of neurofibromin also activates extracellular signal-regulated-1/2 (ERK 1/2), affecting its interaction with mitochondrial chaperone tumor necrosis factor receptor associated protein 1 (TRAP1), decreasing succinate coenzyme Q reductase(10,27). Although NF1 animal models show mitochondrial dysfunction, literature evaluating mitochondrial function in patients with NF1 is scarce. Another factor possibly impacting mitochondrial function is the use of MEK inhibitors. These drugs are the only FDA-approved treatment for plexiform neurofibroma, a type of tumor that grows in the nerves of NF1 patients. MEK inhibitors can cause an increase in the oxygen consumption rate, and they can alter the mitochondrial metabolism affecting complex I and the electron transport chain (24,29). **We hypothesize that NF1 patients exhibit a range of MD that contributes to adverse health outcomes.** Validation of this hypothesis will establish a bioenergetic phenotype among NF1 patients to better stratify them than current clinical descriptions. This information will then be used for identifying relationships between patient symptoms and mitochondrial function to demonstrate its value in the clinic (Aim 1). Further, patient mitochondrial function will serve as an important mechanistic readout on the consequences of neurofibromin mutations and impacts of other factors including lifestyle, diet, and drugs (like MEK inhibitors) that can improve or harm mitochondrial function (Aim 2). These findings would expand beyond the current limitations of results from model neurofibromin knockout studies to more relevant complexities observed with patients. Taken together, information gained from patient mitochondrial function assessments would create opportunities to develop more personalized, targeted therapeutic interventions for improving patient outcomes.

The mitochondrial function in patients with NF1 and how it correlates with clinical symptoms will be investigated for the first time in this proposed study. This novel experimental design will generate more clinically relevant findings in humans than current in vitro and in vivo animal studies. Moreover, the strategy leverages a minimally invasive blood test using peripheral blood mononuclear cells (PBMCs) to assess mitochondrial function. Studies with PBMCs detected metabolic stress in patients and acted as biomarkers for MD in diseases including diabetes (22), neurodegenerative disease (23), cardiovascular disease (21), as well as many cancers (14–16). The proposed study will be the first demonstration of PBMCs as biomarkers for MD for NF1 patients. This new technique will expand the phenotyping toolbox for patients to include

bioenergetic demands due to the disease as well as in response to interventions like the growing field of MEK inhibitors for NF1 treatment (1,4,24). This pilot project's candidate biomarker approach on mitochondrial function focuses on clinically relevant questions such as fatigue, pain, cardiac, and renal function. However, our results could be correlated with other important NF1 phenotypes and even data from future systemic unbiased multi-omics approaches to interpret their meaning within patient bioenergetics.

### **Hypothesis and/or Specific Aims or Objectives**

Neurofibromatosis 1 (NF1) is one of the most common hereditary tumor predisposition syndromes afflicting ~1 in 2750 people worldwide (1,2). Hallmark traits include peripheral and central nervous system tumors along with skin and eye lesions, cognitive deficiencies, musculoskeletal abnormalities, and multiple types of cancer (2,3). The clinical phenotype arises from point mutations (90%) and deletions of the NF1 tumor suppressor gene encoding neurofibromin (4). A well-characterized neurofibromin function is stimulation of Ras GTPase activity leading to Ras inactivation and suppression of its signals through multiple effectors, including mTOR, MEK, ERK, and potentially cAMP/PKA indirectly (5–7). Emerging evidence suggests that neurofibromin regulates cellular and organismal metabolism. The decreased respiratory quotients (ratio of eliminated CO2 to consumed O2) reported for NF1 patients implicate neurofibromin defects as a source of altered basal metabolic rates (8). Similarly, animal knockout models have reduced respiratory quotients and increased energy expenditures (9–11). Further analysis of isolated cells lacking neurofibromin show lower basal and coupled respiration, lowered maximal and spare respiratory capacities, and elevated reactive oxygen species, underscoring the importance of neurofibromin on mitochondrial function (10). Supplementation with L-carnitine, a mitochondrial nutrient important for fatty acid oxidation and gluconeogenesis, improved weakness and fatigue in NF1 patients (12,13). Due to a diverse array of genetic lesions, **we hypothesize that NF1 patients exhibit a range of mitochondrial dysfunction (MD) as contributing factors to adverse health outcomes.** We will test the hypothesis by isolating peripheral blood mononuclear cells (PBMCs) from NF1 patients recruited through the new Adult UAMS Neurofibromatosis Clinic at the Winthrop P. Rockefeller Cancer Institute and measure mitochondrial function for correlative studies with clinical phenotypes and symptoms. While novel for NF1 patient studies, the use of PBMCs for mitochondrial studies has precedence in assessing function with a variety of cancers and other diseases (14–23). The effort for this NF1 pilot study involves expertise in pathogenesis and treatment of NF1 ([name]), mitochondrial biology ([name]), and metabolism ([name]) to achieve the following aims:

#### **Aim 1: Demonstrate mitochondrial respiration efficiency of PBMCs inversely correlates with clinical symptoms of NF1 patients.**

We will use an Agilent Seahorse XF Pro Analyzer to measure the cellular and mitochondrial bioenergetics of PBMC isolated from NF1 patients. We predict patients with milder symptoms of fatigue, pain, liver and cardiac function, creatine kinase (CK), and body mass index (BMI) will demonstrate better mitochondrial function in their circulating cells.

**Aim 2: Assess whether therapeutic interventions impact mitochondrial function and metabolic plasticity of circulating cells of NF1 patients.**

We hypothesize that MD among NF1 patients sensitizes them to therapeutic interventions targeting mitochondria. We will assess the impact of vitamin D treatment to potentially improve mitochondrial function and explore if MEK inhibitors like Koselugo (KOS, Selumetinib, FDA-approved treatment of plexiform neurofibromas in NF1) harm mitochondrial function in patients with NF1, due to their impact in the RAS pathway (24). We predict that the impact of treatments on mitochondrial function will lead to insights on mechanisms of action for NF1 patients and possibly serve as diagnostic and/or prognostic biomarkers for patient outcomes.

Preliminary findings will demonstrate a powerful, novel approach for assessing and understanding the differences in bioenergetic status among NF1 patients and open new research venues. The next steps will study the degree of MD and its correlation with 1) different NF1 mutations (deletions, truncations), 2) other NF1 complications like cognition outcome and quality of life, and 3) prevalence and prognosis of cancers.

Hence, this proposal will generate future projects that will aid the team in achieving the long-term goal of determining mechanisms driving NF1 clinical phenotypes and symptoms to stratify and treat patients. To that end, this pilot study will foster a collaborative team across disciplines and departments at UAMS to leverage the first and only neurofibromatosis clinic in Arkansas at UAMS for improving adult NF1 patient care, and also expand the spectrum of research done by the Drs. [name] and [name], who have not researched populations with genetic diseases so far, and [name], who has not researched mitochondrial function.

**Study Design and Procedures (sometimes called “Methods”)**

Although all NF1 patients have genetic changes in the same gene, the clinical presentations of the disease are widely diverse. Thus, it is important to determine non-invasive biomarkers that would help stratifying NF1 patients, who present with highly variable and unpredictable clinical manifestations. Some of the comorbidities seen in NF1 are also shared with patients with mitochondrial diseases (e.g., short stature, fatigue, pain). Thus, our main goal will be to demonstrate a co-association of clinical symptoms and MD that exists in these patients.

**Aim 1: Demonstrate that mitochondrial respiration efficiency of PBMCs inversely correlates with clinical symptoms of NF1 patients.**

Parameters associated with MD of PBMCs will be assessed as potentially shared cellular pathology in NF1 patients. We hypothesize that MD based on parameters (e.g., coupling efficiency and respiratory capacity) positively correlates with more adverse outcomes as reflected in the symptoms of fatigue, pain, liver, kidney, and cardiac function. Patients over 18 years old, previously diagnosed with NF1, will be eligible for this project. A subject will be registered in the study only after obtaining a signed copy of the Informed Consent Form, completing all pretreatment evaluations, meeting all eligibility criteria, and presenting no exclusion criteria. The neurofibromatosis clinic at UAMS currently cares for 100 patients a year, and it is in a phase of expansion. It is expected that the clinic will see 100 to 140 patients in the next year. We will also recruit 10 to 15 healthy individuals as the control group. Mitochondrial function and cellular bioenergetics will be measured in PBMCs and platelets isolated from blood collected at consent and every 3-4 months for one year. Freshly isolated cells will be plated in coated XF96-Pro well plates using assay media, and the plate will be centrifuged. After the

attachment is confirmed, the cells will be then incubated in a non-CO2 incubator for 20 min at 37°C. The cellular bioenergetics of PBMCs or platelets will be determined by using a standard mitochondrial stress test as we previously published via consecutively injecting oligomycin, an uncoupler (FCCP), and the mitochondrial electron transport chain blockers antimycin A and rotenone into the wells as we previously published (30–37). Clinical repercussions of MD in NF1 will be measured through serial scores of fatigue and pain on the same days that PBMC and platelets are collected. Fatigue will be assessed through the Functional Assessment of Chronic Illness Therapy-Fatigue (FACIT-F). FACIT-F is the only fatigue scale that has been validated in dermatological and painful disease, as it is commonly used in neurological disorders (38). Pain will be assessed by the NRS-11 scale, as recommended by the patient-reported outcome group of the Response Evaluation in Neurofibromatosis and Schwannomatosis (REIS) (39). Other biochemical and metabolic functions to be followed will be CK, cardiac function through echocardiogram, body mass index, liver, and kidney function.

**Aim 2: Assess whether therapeutic interventions impact mitochondrial function and metabolic plasticity of circulating cells of NF1 patients.** We hypothesize that NF1 patients' inherent mitochondrial dysfunction makes them more responsive to therapeutic interventions resulting in further mitochondrial injury (e.g., by MEK inhibitors, including KOS) or improved function (e.g., by vitamin D). Most patients are vitamin D deficient so the standard of care involves supplementation that could improve mitochondrial function given its essential role in many related processes. Also, we will carry out an exploratory study on the potential adverse effects of KOS on adult NF1 patients who are beginning therapy during the study window. While promising in treatment, the use of this drug has a high incidence of significant adverse side effects like cardiotoxicity (30%). The cause for toxicity is unknown yet may involve further compromised mitochondrial function as reported for other similar tyrosine kinase inhibitors (40). The combination of these studies will provide a critical preliminary assessment of the sensitivity of the mitochondrial measures to patient interventions as well as the possible capacity to correlate with favorable or harmful outcomes.

Subjects who present to the clinic and match the inclusion/exclusion criteria for either the NF1 or control group will be provided a copy of the consent for review. A thorough discussion of the consent will be provided by study staff. If the subject agrees to participate, the following will be completed at each of the 3 total visits required by the study. Each visit will occur at 14 weeks (+/- 2 weeks):

### Visit 1

- The subject's medical history will be gathered. This will include information regarding a subject's height, weight, medications used, vitamin D levels, kidney, liver, and heart function.
  - For control subjects, the PI will confirm that the subjects do not have NF1 by family history and physical exam.
- Questionnaires regarding pain and fatigue will be provided for the subject to review and answer.
- Standard-of-care lab draws will continue to occur.
- An additional 10 mL of blood will then be drawn for mitochondrial testing purposes.

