## **Study Population**

This study will look to enroll 40 to 45 adults over 18 years old diagnosed with NF1 as well as 10 to 15 adults over 18 years old without NF1 (the control group).

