### Exclusion Criteria

- NF1 group
  - Under 18 years old
  - Not agreeable to participating in the study
- Control group
  - Under 18 years old
  - Diagnosed with NF1
  - The first degree relative (biological parent, sibling, or child) of an NF1 patient who is participating in the study

Examples of recruitment methods include, but are not limited to the following:

- Patients with NF1 at the UAMS Adult NF1 clinic will be invited to participate in the study during their regular clinic appointments. If the patient is interested in participating in the study, a Cancer Clinical Trial Office nurse will be called to consent the patient.
- Spouses, friends, and non-relatives of NF1 patients who come to the UAMS Adult NF1 Clinic will be invited to participate in the control arm of the study at the time of the patient appointment. If the non-patient is interested in participating in the study, a Cancer Clinical Trial Office nurse will be called to consent the control group volunteer. They will then receive a single blood draw at the time of consent.

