### **Specimen Handling and Storage**

Blood samples will be collected from patients and controls during routine appointments. Samples will be given a unique identifying number, and then transported to [name] laboratory where they will be tested and stored. A key linking the coded sample to the data will be maintained separately on a UAMS password-protected server. Transport will be done by Drs [name] laboratory staff.

If the patient sample volume is not completely used for this project, it will be retained for further study if patient indicates so in the consent. This sample might be used for future research to study the pathophysiology of neurofibromatosis. In the case that there is an opportunity to use the storage blood, we will decode data and enter in contact with patient to request their consent for the new project.

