### **Data Analysis**

XF Pro mito-stress test data will provide direct measurements of basal, nonmitochondrial, and maximum respiration, and we will use these data to calculate the mitochondrial basal respiration, ATP-linked respiration, reserve respiratory capacity, proton leakage, and coupling efficiency in PBMCs and platelets isolated from the control group once and from NF1 patients longitudinally (3 times). At the end of each run, we will also determine the cellular bioenergetics and metabolic plasticity (switch between oxidative phosphorylation and glycolysis) of the cells via plotting extracellular acidification rate versus oxygen consumption rate. The NF1 and healthy control groups' mitochondrial function and metabolic plasticity parameters will be compared in addition to longitudinal changes in these parameters for each NF1 patient. Linear regression analysis will be utilized to establish the relationship between coupling efficiency, respiratory capacity (ATP-linked, reserve capacity etc.) as well as metabolic plasticity and NF1 clinical phenotype and biochemical scores for fatigue, pain, CK, cardiac function, BMI, and liver function. Analysis of variance for repeated measures will also be used to analyze changes in these parameters over time by each group (NF1 patients before and after Vitamin D and/or KOS administration).

This pilot study was designed to test the feasibility of our recruitment and implementation procedures and operational strategies. Preliminary data obtained from this pilot project will also be used to assess the variability of outcomes for power analysis of future larger studies. A biostatistician will be consulted during pilot data analysis and included in the team for statistical power calculations for future studies.

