## **Ethical Considerations**

This study will be conducted in accordance with all applicable government regulations and University of Arkansas for Medical Sciences research policies and procedures. This protocol and any amendments will be submitted and approved by the IRB as required.

No compensation will be given for patients or controls.

The informed consent of each subject, using IRB-approved consent materials, will be obtained before that subject begins any study procedures. All subjects for this study will be provided a paper consent form describing this study in language understandable to the study population. Consent materials will provide sufficient information for subjects to make an informed decision about their participation in this study. The person obtaining consent will thoroughly explain what the subjects need to know about the study, including study requirements, study risks and benefits. The consent process will take place during their clinic visit in the exam room. The consent discussion will occur at the same day of the first blood sample. Participant privacy will be maintained and questions regarding participation will be answered. No coercion or undue influence will be used in the consent process. This consent form must be signed by the subject, and the person obtaining the consent. The participant will receive a paper copy of the signed consent form, and the informed consent process will be documented in the research record.

The consent process will be documented separately via a written note in the research or medical chart for each subject.

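### Cells are assayed fresh over many Seahorse runs, but the plan neither co-plates companion controls with same-day patients nor records or models run; the likely cost is mainly precision

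*Combined protocol and SAP*

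**What the plan says.** - **Assay.** Study Design and Procedures, Aim 1: "Freshly isolated cells will be plated in coated XF96-Pro well plates using assay media, and the plate will be centrifuged". No freezing for a later batch assay is described.
- **Timing.** The same section has cells "isolated from blood collected at consent and every 3-4 months for one year". Specimen Handling and Storage adds: "Blood samples will be collected from patients and controls during routine appointments". The sampling day therefore follows the clinic diary, not an assay batch.
- **Controls.** In the recruitment list under Exclusion Criteria, spouses, friends and non-relatives of patients "will be invited to participate in the control arm of the study at the time of the patient appointment". "They will then receive a single blood draw at the time of consent". Ethical Considerations confirms the timing: "The consent discussion will occur at the same day of the first blood sample".
- **Numbers.** The Study Population section reads: "This study will look to enroll 40 to 45 adults over 18 years old diagnosed with NF1 as well as 10 to 15 adults" without NF1.
- **Analysis.** Data Analysis says that the two groups' "mitochondrial function and metabolic plasticity parameters will be compared in addition to longitudinal changes" within NF1 patients. No test is named for the group comparison. Repeated-measures analysis of variance is named for change over time. Neither has a term for run, plate or day. The word run appears only in connection with the acidification-versus-oxygen plots.

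The documents do not mention shared plating, a reference sample per run, between-run normalisation, recording of run, or spreading controls over accrual.

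**The concern.** Each run brings its own plate, reagents and inhibitor injections, so samples in the same run share whatever error that run carries. Two things follow for the NF1-control difference.

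First, run variance adds to the error of the difference unless controls and patients share runs, in which case part of it cancels. Companion controls make sharing possible at almost no cost, but the plan does not ask for it.

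Second, if the 10 to 15 controls were recruited on a handful of days, they would share a few run errors. An analysis that omits run would then give a standard error that is too small. Better-matched controls would not cure this, because it arises from the assay layout.

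The longitudinal analyses are exposed too: visits 2 and 3 fall in later runs, and controls are drawn only once. The pilot is also meant to supply variability for later power calculations. Without run identifiers, between-run and between-person variance cannot be separated.

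**Working it through.** The plan gives no alpha, power, SD or between-run variance, so there is no figure of its own to reproduce. What follows is illustrative.

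**Inputs from the documents:** 40 to 45 NF1 patients and 10 to 15 controls; I use 42 and 12.

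**Assumptions:** two-sided 5% test; one result per person; two patients per run, so 42/2 = 21 patient runs; within-run person variance 1; run variance v = 0.25, 0.5 or 1.

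**Variance of the difference in means, run left out of the analysis.** The person part is 1/12 + 1/42 = 0.107. With controls spread evenly over k runs, the run part is:

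- control runs containing no patients: v/k + v/21
- control runs that are also patient runs: v/k + v/21 − 2v/21 = v/k − v/21

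For v = 0.25/0.5/1:

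- 12 separate control runs: 0.107 + v(1/12 + 1/21) = 0.140/0.173/0.238
- 12 shared runs: 0.107 + v(1/12 − 1/21) = 0.116/0.125/0.143
- 3 shared runs: 0.107 + v(1/3 − 1/21) = 0.179/0.250/0.393
- 3 control-only runs: 0.107 + v(1/3 + 1/21) = 0.202/0.298/0.488

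**Each control co-plated, run modelled as a random effect (generalised least squares, v known).** There are 12 runs with one control and two patients, and 9 with two patients. Let w3 = v/(1+3v) and w2 = v/(1+2v). The information terms are:

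- A = 12(1 − w3) for the control mean
- B = −24·w3 for the cross term
- C = 12(2 − 4·w3) + 9(2 − 4·w2) for the patient mean

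The variance of the difference is (A + C + 2B)/(AC − B²). At v = 1: w3 = 1/4, w2 = 1/3, A = 9, B = −6, C = 18, giving 15/126 = 0.119. At v = 0.25 and 0.5 it is 0.113 and 0.116.

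**Gain from co-plating and modelling:**

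- against 12 separate control runs: 1 − 0.113/0.140, 1 − 0.116/0.173 and 1 − 0.119/0.238 = 19/33/50%
- against 12 shared runs with run left out: 1 − 0.113/0.116, 1 − 0.116/0.125 and 1 − 0.119/0.143 = about 3/7/17%

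**Type I error of an unadjusted t-test (simulation):**

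| Where the 12 controls fall | v = 0.25 | v = 0.5 | v = 1 |
|---|---|---|---|
| One in each of 12 patient runs | about 4% | about 3% | about 2% |
| Two in each of 6 patient runs | 5% | 6% | 6% |
| 12 runs of their own | about 6% | about 6% | about 6.5% |
| Four in each of 3 patient runs | 9% | 12% | 15% |
| Four in each of 3 control-only runs | 11% | 15% | 20% |

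**How far pairing can reach.** At one visit, between 10/45 = 22% and 15/40 = 38% of NF1 patients could have a same-day control.

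**The case against.** The strongest reply is that the recruitment route already limits the problem. Controls are companions drawn at a patient's appointment, so a control will usually be on site on a patient's day. Study Design and Procedures expects 100 to 140 patients a year, or about 2 to 3 a week if evenly spread (100/52 = 1.9; 140/52 = 2.7). Twelve controls over three days, on plates without patients, is then improbable. In the likelier layouts the unadjusted test is conservative or close to nominal. This stands, and it makes the control-only row a worst case.

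A reader might infer that the plan treats all results as coming from one run. The documents do not say so. Data Analysis names no method for the group comparison and promises a biostatistician during pilot data analysis; the gap is silence, not a stated choice. They also do not say that same-day samples go on separate plates, so some sharing may happen anyway. But a biostatistician consulted at analysis cannot change plate layout or recover run identifiers that were never kept.

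A reader might also take the NF1-control contrast as what the study stands on. The stated main goal is co-association of symptoms and mitochondrial dysfunction in NF1 patients, and Aim 2 concerns change within NF1 patients. The group contrast is secondary, in a feasibility pilot with no confirmatory test.

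Finally, run variance is poorly identified when a run holds one sample, which is plausible at this clinic volume. That also stands and limits what the run term can deliver.

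**Conclusion.** The gap is real and holds as a cheap improvement to design and analysis. Fresh assay on clinic days means many runs, and the plan provides for neither co-plating, recording of run nor a run term.

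The size depends wholly on an assumed run variance of 0.25 to 1 times the within-run person variance. The gain from co-plating and modelling lies between about 3/7/17% and 19/33/50% of the variance of the difference, depending on whether same-day samples would share a run without being told to.

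The tempting stronger reading is that the NF1-control comparison will be biased or carry a false-positive rate of up to 20%. The documents do not support that. It needs controls packed into a few runs without patients, which the companion recruitment route makes unlikely. Nothing prevents clustering, though, and 9/12/15% in three shared runs shows why it should be ruled out by design. The main benefits are precision, correct standard errors and a usable variance breakdown for later studies.

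**What to change.** **Study Design and Procedures, and the recruitment list under Exclusion Criteria:** state that control invitations will be spread over the accrual period. State also that, when the companion's patient gives a study sample that day, both samples go on the same XF96 plate.

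**Data Analysis:** record run/plate identifier and date for every sample. Include run as a random effect in the NF1-control comparison and in the longitudinal models. Report between-run variance separately, using runs that hold more than one sample, because the pilot's variability feeds later power calculations. Keep all samples in the model instead of restricting to same-plate pairs: with 12 pairs only, the variance is 2/12 = 0.167, against 0.113 to 0.119 with everyone included.

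**Cost:** a plate-layout rule, two data fields and one model term; no extra draws or participants. Plate space must be reserved for both samples and control scheduling is somewhat constrained. Run variance will be imprecise if many runs hold a single sample. A common reference sample in each run would help there, at the price of extra laboratory work, and could be considered.
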